## 1 Abbreviations

AE	adverse event
ETDRS	early treatment diabetic retinopathy study
IBI	interblink interval
IER	Institute of Eye Research
IOP	intraocular pressure
OPI	ocular protection index
OSDI	ocular surface disease index
ITT	intent-to-treat
PP	per-protocol
SADE	serious adverse device effect
SAE	serious adverse event
SAP	statistical analysis plan
TBUT	tear film break-up time
USADE	unanticipated serious adverse device effect
ANOVA	Analysis of variance
MedDRA	Medical dictionary of regulatory authorities

## 2 Study objective(s)

The study is comprised of three parts. Part 1 of the study aims to investigate safety and ocular tolerability of trehalose emulsion eye drops. Primary objective of Part 1 of the study is:

*to evaluate the safety and ocular tolerability of trehalose emulsion eye drops administered on one eye four times a day for one day.*

Part 2 of the study aims to investigate the safety, ocular tolerability and efficacy of trehalose emulsion eye drops administered for 10 days compared to control eye drops. Primary objective of Part 2 of the study is:

*to evaluate the safety, ocular tolerability and efficacy (OSDI, tear osmolarity, tear film break-up time) of trehalose emulsion eye drops administered on both eyes three times a day for 10 days as a change from baseline and compared to control eye drops.*

The secondary objective of Part 2 of the study is:

*to evaluate the efficacy (blink rate, corneal and conjunctival staining) of trehalose emulsion eye drops administered on both eyes three times a day for 10 days as a change from baseline and compared to control eye drops.*

Part 3 of the study aims to investigate the safety, ocular tolerability and efficacy of trehalose emulsion eye drops administered for 30 days compared to control eye drops. Primary objective of Part 3 of the study is:

*to evaluate the safety, ocular tolerability and efficacy (OSDI, tear osmolarity, tear film break-up time) of trehalose emulsion eye drops administered on both eyes three times a day for 30 days as a change from baseline and compared to control eye drops.*

The secondary objective of Part 3 of the study is:

*to evaluate the efficacy (blink rate, corneal and conjunctival staining) of trehalose emulsion eye drops administered on both eyes three times a day for 30 days as a change from baseline and compared to control eye drops.*

### **3 Design and type of the study**

This is a prospective, single-site, randomized, active-controlled, parallel, double-blind, single and multiple dose study to evaluate the safety, ocular tolerability and efficacy of Piiliset Trehalose Emulsion Eye Drop in the adult patient population with moderate or severe dry eye for up to 30 days.

### **4 Sample size considerations**

A total number of 64 adult patients (both males and females) will be included in the study as follows:

In Part 1 of the study, a total of 3 subjects to obtain preliminary information on the acute safety and ocular tolerability of the treatment from all 3 completing subjects (n=3). In Part 2 of the study, nine subjects to obtain preliminary information on the long-term safety, ocular tolerability, and efficacy of the daily treatments from at least 8 completing subjects (n=8). In Part 3, 52 subjects to obtain information on the long-term safety, ocular tolerability, and efficacy of the daily treatments from at least 44 (83%) completing subjects allocated in two randomized treatment groups (n=22).

No subject will be allowed to participate in more than one Part of the study.

### **5 Statistical hypotheses**

The purpose of this study is to evaluate ocular safety and tolerability in 3 different study Parts conducted sequentially. For the study part 3 a sample size calculation was conducted with OSDI as the parameter of interest. The evaluation of the study will be based on the total evidence collected.

The null-hypothesis to be tested is

$H_0$  : There is no difference between study products in OSDI scores.

$H_1$  : There is a significant difference in OSDI scores in favour of the investigational product.

Statistical analyses will be performed primarily on the ITT population. The PP population will be used as a secondary dataset.

## **6 Analysis sets**

### **6.1 Intention-to-treat (ITT) set**

The ITT population includes all randomized subjects who have received the study medication at least once and who have subsequent efficacy measurements available.

### **6.2 Safety dataset**

The safety population will include all randomized subjects who have received the study medication at least once from whom at least one safety measurement is obtained after randomization.

### **6.3 Per protocol (PP) set**

The PP population excludes subjects with significant protocol deviations, including withdrawn subjects. Protocol deviations will be assessed prior to database lock.

## **7 General statistical considerations**

The aim of study is to investigate the safety, ocular tolerability and efficacy of Piiliset Trehalose Emulsion Eye Drop in adult patients with moderate or severe dry eye.

No imputations will be done for missing observations. If not stated otherwise, a two-sided p-value less than 0.05 will be considered statistically significant.

No interim analyses are planned.

## **8 Demographic and other baseline characteristics**

The comparability of the treatment groups will be assessed by the demographic and baseline characteristics. These include but are not restricted to

- Age
- Gender
- Weight
- History of ocular surgery, trauma, refractive laser vision correction, infection, allergy
- Topical and/or systemic therapies for the preceding 4 weeks
- Allergy to any constituent of the investigational
- Current or planned pregnancy and nursing

---

Demographic and baseline characteristics of the subjects will be tabulated with descriptive statistics. The disposition of the subjects (and eyes) will be summarized.

## **9 Concomitant medication/treatment**

Concomitant medications reported during the study will be listed.

## **10 Extent of exposure and compliance**

Exposure and compliance will be reported descriptively using the information available in the database.

## **11 Analysis of efficacy**

### **11.1 Primary efficacy variables**

#### **11.1.1 OSDI**

The OSDI questionnaire comfort rating used as an efficacy endpoint will be performed

- before the 1st treatment in all Parts; and
- at end-of-study visit in Parts 2 (Day 10) and 3 (Day 30).

#### **11.1.2. Biomarkers**

Biomarkers to be assessed as primary efficacy endpoints will be determined

- at screening visit;
- before the 1st treatment in all Parts; and
- at end-of-study visit in Parts 2 (Day 10) and 3 (Day 30).

Biomarkers used as primary efficacy endpoints are a part of the physical examination of the eyes and include the following methods:

- tear osmolarity
- tear film break-up time (TBUT)

Ocular comfort ratings (OSDI) by the subjects will be summarized by study day and treatment (Parts 2 and 3). The results will be presented separately for Parts 2 and 3.

The comparisons between treatment groups in Part 2 after ten days treatment will be conducted using standard statistical methodology for paired data (e.g. paired t-test for continuous variables and Wilcoxon signed rank test for variables in ordinal scale) between eyes (study treatment administered in other eye and control treatment to contralateral eye).

The comparisons between treatments in all ocular measurements (including biomarkers and physical examination of eye parameters) in Part 3, which are the primary basis of evaluation of study objectives, are done using the parallel group design. Analysis of variance model will be used to evaluate the difference in the change from baseline in OSDI between treatment groups. Similar method will be used for tear osmolarity and tear film break-up time. In case the normality assumption is violated then Wilcoxon rank sum test will be used instead.

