Part 2. One drop 3 times a day on a randomized eye for 10 (\pm 1) days at home

Part 3. One drop of the randomized product 3 times a day on both eyes for 30 (\pm 2) days at home

Assessments:Safety and ocular tolerability:

Physical examination of the eyes will be performed by the Investigator at screening, in Part 1 at baseline and after the 4th dose, in Parts 2 and 3 at baseline and after the last dose. The Investigator will also evaluate possible local eye reactions visually at visits in all Parts.

Ocular comfort rating using the OSDI questionnaire will be performed at screening, before the 1st treatment in all Parts, and at end-of-study visit in Parts 2 and 3.

AEs will be collected throughout the study.

Efficacy:

OSDI, tear osmolarity, TBUT, blink rate, and corneal and conjunctival staining will be measured at screening, before the 1st treatment in all Parts, and at end-of-study visit in Parts 2 and 3.

Statistical methods:

Descriptive statistics by treatment group and visit day will be provided to summarize the results. Also changes from baseline will be summarized with descriptive statistics. No imputations will be done for missing observations. If not stated otherwise, a two-sided p-value less than 0.05 will be considered statistically significant. Changes in OSDI scores in Part 3 will be compared by treatment groups using analysis of variance model. No interim analyses are planned.

ABBREVIATIONS AND DEFINITION OF TERMS

ADE	adverse device effect
AE	adverse event
CRF	case report form
D	day
EC	ethics committee
FDA	Food and Drug Administration
GCP	good clinical practice
ETDRS	early treatment diabetic retinopathy study
IB	investigator's brochure
IBI	interblink interval
IER	Institute of Eye Research
IOP	intraocular pressure
ITF	investigator's trial file
OPI	ocular protection index
OSDI	ocular surface disease index
ITT	intent-to-treat
PP	per-protocol
SADE	serious adverse device effect
SAE	serious adverse event
SAP	statistical analysis plan
SD	standard deviation
TBUT	tear film break-up time
TFOS DEWS II	Tear Film and Ocular Surface Society's Dry Eye Workshop II
USADE	unanticipated serious adverse device effect

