3.2.1. Randomization and blinding

Part 1. No randomization or blinding will be used.

Part 2. The randomized test item will be administered on a randomized eye of the subject in a double-blinded fashion. The randomization will be balanced for the right and left eyes.

Part 3. The test item will be administered on both eyes of the randomized subject in a double-blinded fashion. The randomization will be balanced for the gender of the subjects.

Randomization lists will be prepared and stored at 4Pharma. The code envelope will be opened prematurely on the Investigator's resolution in cases of emergency.

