The subjects arrive at the study centre on Day 10 (\pm 1) for an end-of-study visit. Only the morning dose will be administered on the same day. Physical examination of the eyes, digital photography of the anterior parts of the eyes, and ocular assessments including OSDI, tear osmolarity, blink rate, corneal and conjunctival staining, and TBUT are performed. In addition, the subjects are asked to return the used eye drop bottles. The study diaries are collected, checked, and marked on case report forms (CRFs).

Possible AEs and other study-related issues are monitored and discussed with the subjects and recorded. Any abnormal findings will be assessed according to their clinical importance and, if found to be possibly clinically significant but not study-related, the subject is instructed to contact his/her own health care provider.

The participants are not allowed to enter Part 3. Possible discontinued subjects will be invited to an end-of-study visit which should be performed within one week after the date of discontinuation, if possible.

Part 3. The subjects arrive at the study centre at an agreed time in the morning on Day 1. Physical examination of the eyes, digital photography of the anterior parts of the eyes, and baseline assessments including OSDI, tear osmolarity, blink rate, corneal and conjunctival staining, and TBUT are performed. The subjects self-administer one drop of the randomized treatment eye drop (either Piiloset Trehalose Emulsion Eye Drop or the control eye drops) on both eyes under control of the Study Nurse. The subjects then receive the treatment eye drop bottle to themselves with detailed instructions on how to continue dosing at home three times a day for the next 30 (\pm 2) days, including Day 1. The subjects are urged to contact the study personnel in case of an AE, especially in the ocular area before Day 30. They will be invited to visit the study site when clinically indicated, based on the judgement of the Investigator. The subjects may then leave the study centre.

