7.1. Estimation of sample size

Sample sizes in Parts 1 and 2 of this study are based on clinical considerations with no formal sample size calculation. The number of subjects planned to be included in Part 3 is based on expected mean OSDI values shown in Table 3 below. The estimated minimum number of patients completing the study in one treatment group is 23 based on the sample size calculation. Sample size was calculated using nQuery advisor software (version nQuery + nTerim 3.0).

A total number of 64 adult patients (both males and females) will be included in the study as follows:

Part 1. 3 subjects to obtain preliminary information on the acute safety and ocular tolerability of the treatment from all 3 completing subjects (n=3).

Part 2. 9 subjects to obtain preliminary information on the long-term safety, ocular tolerability, and efficacy of the daily treatments from at least 8 completing subjects (n=8).

Part 3. 52 subjects to obtain information on the long-term safety, ocular tolerability, and efficacy of the daily treatments from at least 46 (88%) completing subjects allocated in two randomized treatment groups (n=46).

Table 3. Parameters used in sample size estimation for Part 3

Parameter	OSDI at D1 (baseline)	OSDI at D30 (end of study)	SD
Study treatment group	36	12	14
Control group	36	24	14
Two-sided significance (α)	0.05		
Power (1- β)	0.80		
Total sample size required	46		
Sample size required per group	23		

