7.2.5. Analysis of study variables

Demographic and baseline characteristics of the subjects will be tabulated with descriptive statistics. The disposition of the subjects (and eyes) will be summarized.

The safety population having received the study treatment and with any follow-up data will be considered evaluable for safety and tolerability for the corresponding Part of the study. AEs will be summarized for each treatment group and study Part by severity, causality, and duration. Ocular AEs will be reported separately. All SAEs will be listed with all relevant information.

In Part 1, the ocular safety and tolerability of trehalose emulsion eye drops will be evaluated as a within-subject comparison to the untreated eye and to baseline. In Part 2, the evaluation will be performed as a within-subject comparison to the control eye and to baseline. In Part 3, the evaluation will be performed between subjects receiving trehalose emulsion eye drops in comparison with subjects receiving control eye drops and to baseline.

Physical examination of the eye parameters will be summarized descriptively by eye in all Parts of the study. The ocular safety and tolerability of the treatments evaluated at the end-of-study visit will be summarized by study day, treatment and eye. In addition, ocular comfort ratings (OSDI) by the subjects will be summarized by study day and treatment (Parts 2 and 3).

The comparisons between treatments in Part 2 will be conducted using standard statistical methodology for paired data (e.g. paired t-test for continuous variables and Wilcoxon signed rank test for variables in ordinal scale). The comparisons between treatments in all ocular measurements (including biomarkers and physical examination of eye parameters) in Part 3, which are the primary basis of evaluation of study objectives, are done with statistical methods appropriate for parallel group design. Analysis of variance technique will be used to evaluate the difference in the change in OSDI between treatment groups. Wilcoxon rank sum test will be used for ordinal scale variables (e.g. staining and redness). Details of all methods and the testing strategy will be provided in the SAP finalized before the database lock and randomization code opening.

Concomitant medications will be listed.

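### The Part 3 OSDI analysis is an ANOVA of change with no baseline or gender term, and Table 3 does not label its SD of 14; a prespecified ANCOVA holds power at about 80% or more with 23 per group under either reading.

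*SAP*

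**What the plan says.** The protocol synopsis (Statistical methods) states: "Changes in OSDI scores in Part 3 will be compared by treatment groups using analysis of variance model". Protocol 7.2.5 repeats this: "Analysis of variance technique will be used to evaluate the difference in the change in OSDI between treatment groups". It leaves the rest to the SAP: "Details of all methods and the testing strategy will be provided in the SAP finalized before the database lock and randomization code opening".

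SAP 11.1.2 then gives: "Analysis of variance model will be used to evaluate the difference in the change from baseline in OSDI between treatment groups". It names no covariate or factor. What it adds for OSDI is a fallback: "In case the normality assumption is violated then Wilcoxon rank sum test will be used instead". It gives no check or threshold for deciding that normality has failed.

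Two candidate model terms are already available. On Part 3 randomisation, Protocol 3.2.1 says: "The randomization will be balanced for the gender of the subjects". For Part 3 Day 1, Protocol 3.2.3 says: "baseline assessments including OSDI, tear osmolarity, blink rate, corneal and conjunctival staining, and TBUT are performed".

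On size, Protocol 7.1 says: "The number of subjects planned to be included in Part 3 is based on expected mean OSDI values shown in Table 3 below". Table 3 lists OSDI means of 36 falling to 12 (study product) and 36 falling to 24 (control), with 14 for each group in a column headed only SD. It gives no baseline/Day 30 correlation.

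**The concern.** The 23 per group follows from a difference of 12 and an SD of 14. That calculation describes the planned test only if 14 is the SD of the change from baseline. Table 3 sets the 14 beside mean scores at two visits, so it can equally be read as the SD of the score. Subtracting baseline then adds noise whenever the two visits are weakly correlated, and the stated 80% power may not hold. ANCOVA on Day 1 OSDI avoids this because it estimates how much of the baseline to remove. It also corrects chance Day 1 imbalance, which matters in arms of about 23.

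The normality fallback is a separate prespecification gap. Without a stated rule, the data decide whether the OSDI test is a mean difference or a rank comparison. If the switch happens, the test no longer addresses the mean difference that Table 3 was sized for, and any baseline adjustment is lost as well. No power loss is claimed for the switch.

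**Working it through.** **Inputs.** From Protocol Table 3: difference in mean change (36 − 12) − (36 − 24) = 24 − 12 = 12; SD 14; two-sided α 0.05; power 0.80; 23 per group. From Protocol 3.1: 26 randomised per group. From SAP 4: 22 completers per group. Assumed, because the documents do not give it: the correlation ρ between Day 1 and Day 30 OSDI.

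**Reproducing the plan.** For a two-sample t-test with n per group, the noncentrality is 12 / (SD × √(2/n)). With SD 14, noncentral-t power is 79.3% at n = 22, 81.1% at 23 and 85.8% at 26. The stated 23 per group is therefore reproduced, with 14 as the SD of whichever variable is analysed.

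**Formulas.**
- Reading A: 14 is the SD of the score, equal at both visits. SD of change = 14√(2(1 − ρ)); ANCOVA residual SD = 14√(1 − ρ²).
- Reading B: 14 is the SD of change. The score SD is then 14/√(2(1 − ρ)), so the ANCOVA residual SD = 14√((1 + ρ)/2), again with equal visit SDs.
- ANCOVA power uses 2n − 4 degrees of freedom (treatment, baseline, gender). The residual SD is multiplied by √(1 + 1/(2n − 4)) to allow for chance baseline imbalance; at n = 23 this is √(1 + 1/42).

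**Reading A, 23 per group**

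| ρ | SD of change | Power, change score | ANCOVA SD | Power, ANCOVA |
|---|---|---|---|---|
| 0 | 19.8 | 52% | 14.0 | 80% |
| 0.2 | 17.7 | 61% | 13.7 | 82% |
| 0.3 | 16.6 | 67% | 13.4 | 84% |
| 0.4 | 15.3 | 74% | 12.8 | 86% |
| 0.5 | 14.0 | 81% | 12.1 | 90% |
| 0.7 | 10.8 | 96% | 10.0 | 98% |

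The change-score test reaches 80% only when ρ is at least about 0.49 with 23 per group (0.51 with 22, 0.41 with 26).

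At ρ = 0.3:
- The change-score test needs 31 per group for 80% power. ANCOVA needs 22 (21 gives 79.97%).
- The 95% CI half-width at 23 per group is 2.015 × 16.57 × √(2/23) = 9.8 points for the change score. For ANCOVA it is 2.018 × 13.36 × √(1 + 1/42) × √(2/23) = 8.0 points.

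**Unequal visit SDs under reading A.** The OSDI entry floor of 20 could narrow the baseline spread. Take Day 30 SD 14 and an assumed baseline SD s₀, so that SD of change = √(s₀² + 14² − 2ρ × 14 × s₀). The 80% threshold for the change score is ρ = 0.34, 0.41 or 0.56 for s₀ = 10, 12 or 16. ANCOVA power is unchanged, because its residual SD depends only on the Day 30 SD and ρ.

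**Reading B, 23 per group**

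| ρ | Power, change score | ANCOVA SD | Power, ANCOVA |
|---|---|---|---|
| 0.3 | 81% | 11.3 | 94% |
| 0.5 | 81% | 12.1 | 90% |
| 0.7 | 81% | 12.9 | 86% |

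**Simulation check.** With 20,000 trials per setting and a baseline-only ANCOVA at 23 per group, change score against ANCOVA was:
- Reading A: 52.5% against 80.0% (ρ = 0), 66.6% against 83.8% (0.3), 81.0% against 89.9% (0.5).
- Reading B: 81.3% against 93.7% (0.3), 81.1% against 89.8% (0.5), 81.6% against 86.2% (0.7).

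**Lowest ANCOVA power** (reading A, ρ = 0): 78% at 22 per group, 80% at 23, 85% at 26.

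**The case against.** The strongest reply is that the power loss is conditional twice over. It needs 14 to be the score SD and ρ to be below about 0.49, and the documents establish neither. The protocol and SAP both name change from baseline as the analysed variable, and the sample size reproduces when 14 is its SD. On that consistent reading there is no shortfall. This stands: the unlabelled SD and the unlisted model are facts, while the underpowering is only a risk.

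The remaining objections carry part of their weight:
- An ANOVA of change is valid under randomisation, and the term does not exclude further factors. Both are true. If covariates were intended, one sentence naming them settles the matter.
- The gender term rests on the randomisation scheme. No gain is claimed for it, because the documents give no gender effect on OSDI.
- Protocol 7.2.3 and SAP 5 base the evaluation on all the evidence and put safety and tolerability first. That limits the weight of one test. OSDI in Part 3 is still the only comparison with a formal hypothesis and a sample size.
- Protocol 7.2.4 requires descriptive summaries of change, so mean changes would be reported even after a switch to Wilcoxon. What would be lost is the model-based difference with its confidence interval.

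**Conclusion.** The point holds, and the sponsor should act on it. The Part 3 OSDI model is under-specified and gives up precision that the trial's own data would supply. Table 3 does not show whether the stated 80% power applies to the planned test.

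With 23 per group and a true difference of 12, ANCOVA has about 80% power or more under both readings for every ρ from 0 to 0.8. At the SAP's 22 per group the minimum is about 78%. The change-score test ranges from 52% at ρ = 0 to 81% at ρ = 0.5 under reading A, and has 81% throughout under reading B. All of the gain comes from baseline.

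The exact powers rest on the assumed ρ and, except where shown, on equal visit SDs. The preference for ANCOVA does not. Apart from a small cost in degrees of freedom and chance imbalance, its residual variance cannot exceed that of either the Day 30 score or the change. Confidence is high in the omissions and in this preference; the size of any power loss stays conditional.

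**What to change.** 1. In SAP 11.1.2, make the primary Part 3 OSDI analysis an ANCOVA with treatment, Day 1 OSDI and gender, reporting the adjusted mean difference with its 95% CI.
2. Replace the normality switch with a Wilcoxon rank sum test that is always reported as a sensitivity analysis.
3. State whether the SD of 14 in Table 3 is for the score or the change and, if for the score, the assumed correlation.
4. Record the ANCOVA in SAP 14, which now declares no deviations from the protocol's analyses. If the protocol synopsis and 7.2.5 are amended to match, that entry is not needed.
5. Once the SAP says how two eyes per subject are handled, consider the same baseline adjustment for tear osmolarity, TBUT and blink rate.

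The cost is a few sentences and two model degrees of freedom, with no new data and no more patients. Because Protocol 7.2.5 defers method details to the SAP, a SAP edit with the section 14 entry is enough; the note on the SD can go in SAP 4. Changing the protocol text would follow its own amendment procedure (Protocol 12).

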3. STUDY DESIGN

3.1. Type and design of the study

This is a prospective, single-site, randomized, active-controlled, parallel, double-blind, single and multiple dose study to evaluate the safety, ocular tolerability and efficacy of Piiloset Trehalose Emulsion Eye Drop in the adult patient population with moderate or severe dry eye for up to 30 days.

Part 1. Three subjects (n=3) are dosed with four doses (approximately 2 hours apart) of the emulsion eye drops on the worst eye during office hours of one day at the clinic. The second and third doses will be administered if no signs of significant irritation or other adverse device effect (ADEs) after previous doses are observed by the Investigator.

In the absence of significant ADEs in all patients after the last dose, as assessed by the Investigator, Part 2 will commence.

Part 2. Nine subjects (n=9) self-administer the emulsion eye drops on a randomized eye and the control eye drops on the contralateral eye three times a day for a total of 10 (\pm 1) days. The efficacy end points including

OSDI, tear osmolarity, blink rate, corneal and conjunctival staining, and TBUT will be assessed at baseline (Day 1) and after the last dose (Day 10). The safety and tolerability in both eyes will be evaluated. The patient and the study personnel are blinded to the identity of the study products.

In the absence of significant ADEs in all patients after the last dose, as assessed by the Investigator, Part 3 will commence.

Part 3. Out of 52 subjects, 26 randomized subjects self-administer the emulsion eye drops and 26 subjects apply the control eye drops on both eyes three times a day for a total of 30 (\pm 2) days in a double-blinded fashion. The efficacy end points including OSDI, tear osmolarity, blink rate, corneal and conjunctival staining, and TBUT will be assessed at baseline (Day 1) and after the last dose (Day 30). The safety and tolerability in both eyes will be evaluated.

Adverse events (AEs) will be collected throughout the study. The Investigator will perform the ophthalmologic assessments and will be available for consultation throughout the study.

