3.2.2. Screening

The screening visit will be performed within two weeks before the first dosing day (Day 1). A prospective subject will receive both written and verbal information of the study, an opportunity to ask questions, and sufficient time to consider the decision to participate in the study. Written informed consent will be obtained if the subject decides to participate.

The medical history of the subjects will be recorded by using questionnaire. Physical examination of the eyes, digital photography of the anterior parts of the eyes, and screening assessments including OSDI, tear film break-up time (TBUT), and corneal and conjunctival staining are performed by the Investigator. Subjects are given a study diary to document daily administration of the study treatments, possible AEs, concomitant medications, and any deviations from the instructions given. The diaries are checked and collected at the last visit.

The subjects are included in the study after the results of the screening assessments are available. The Study Nurse will contact the subject and give detailed information on the visit schedule.

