#### A. Physical examination of the eyes

Physical examination of the eyes will be performed

- at screening;
- in Part 1 at baseline (before the 1st dose) and after the 4th dose;
- in Part 2 at baseline (Day 1, before the 1st dose) and after the last dose; and
- in Part 3 at baseline (Day 1, before the 1st dose) and after the last dose.

Methods:

- Visual acuity (ETDRS)
- Digital photography of the anterior eye
- Bulbar redness (IER grading)
- Lid redness (IER grading)
- Intraocular pressure (IOP)

If feasible statistical analysis using similar methods than for efficacy variables can be conducted for these parameters.

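### Part 3 efficacy measures are taken at both screening and Day 1, but the treatment comparisons adjust for neither value, an avoidable loss of precision of uncertain size

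*SAP*

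**What the plan says.** **Two pre-treatment readings.** The efficacy paragraph of the protocol synopsis states that "OSDI, tear osmolarity, TBUT, blink rate, and corneal and conjunctival staining will be measured at screening, before the 1st treatment in all Parts". Table 2 of the protocol marks efficacy assessments at screening and at Part 3 Day 1. Protocol 6.3.2 and 6.4.2 and SAP 11.1.2 and 11.2.1 list screening again for the biomarkers, and Protocol 6.3.1 lists it for OSDI. The two readings are close together: "The screening visit will be performed within two weeks before the first dosing day (Day 1".

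**One is the baseline.** For Part 3, Protocol 3.1 says that the endpoints up to and including "TBUT will be assessed at baseline (Day 1) and after the last dose (Day 30". SAP section 12 places the eye examination "in Part 3 at baseline (Day 1, before the 1st dose) and after the last dose". SAP section 11 never defines baseline for the efficacy model, so Day 1 is inferred from these places.

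**The model.** SAP 11.1.2 sets out an analysis of variance for Part 3: "difference in the change from baseline in OSDI between treatment groups. Similar method will be used for tear osmolarity and tear film break-up time". Blink rate is also analysed by ANOVA. Staining is tested by Wilcoxon rank sum, as are OSDI, osmolarity and TBUT if normality fails. No covariate is named.

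**The concern.** A single Day 1 reading of a symptom score or tear-film sign carries visit-to-visit variation, and a change score takes all of it into the outcome. A Day 1 covariate removes part of that variation. A second pre-treatment reading can remove more, to the extent that it predicts Day 30 beyond what Day 1 already tells us. Both values precede treatment, so adjusting for them does not bias a randomised comparison.

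Precision is what is at stake. Part 3 is sized at 23 completers per arm, with power only just above the 80% target. SAP section 4 speaks of 22 per arm, which falls slightly below it.

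**Working it through.** **1. The plan's own figure.** Protocol Table 3 assumes OSDI falling from 36 to 12 and from 36 to 24, so the difference in change is 24 − 12 = 12 points. It gives SD 14, two-sided α 0.05 and power 0.80. The noncentral t calculation returns 23 per arm, as stated. Power is 81.1% at 23, 79.3% at 22, and 85.8% if all 26 per arm are analysed.

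**2. Notation.** The documents give no between-visit correlations, so everything below is assumed. Let a = corr(screening, Day 1), b = corr(Day 1, Day 30) and c = corr(screening, Day 30). Variances are in units of the single-visit variance, taken as equal at each visit.

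- Change from Day 1 (the plan): 2(1 − b)
- Day 1 as covariate: 1 − b²
- Day 1 and screening as covariates: 1 − (b² + c² − 2abc)/(1 − a²)
- Further cut due to screening: (c − ab)² / [(1 − a²)(1 − b²)]

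The last line is the squared partial correlation of screening with Day 30 given Day 1. It is zero when c = ab, which is what steady (first-order) decay of correlation over time implies.

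**3. Results.**

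| a | b | c | Day 1 only | Day 1 + screening | Further cut |
|---|---|---|---|---|---|
| 0.5 | 0.5 | 0.5 | 0.750 | 0.667 | 11% |
| 0.6 | 0.6 | 0.6 | 0.640 | 0.550 | 14% |
| 0.7 | 0.7 | 0.7 | 0.510 | 0.424 | 17% |
| 0.8 | 0.8 | 0.8 | 0.360 | 0.289 | 20% |
| 0.6 | 0.5 | 0.5 | 0.750 | 0.688 | 8% |
| 0.7 | 0.5 | 0.5 | 0.750 | 0.706 | 6% |
| 0.8 | 0.6 | 0.6 | 0.640 | 0.600 | 6% |
| 0.8 | 0.5 | 0.5 | 0.750 | 0.722 | 4% |
| 0.7 | 0.5 | 0.4 | 0.750 | 0.745 | 1% |
| 0.8 | 0.6 | 0.5 | 0.640 | 0.639 | 0.2% |
| any | any | ab | 1 − b² | 1 − b² | 0% |

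Worked row (0.7, 0.5, 0.5): (0.5 − 0.35)² / (0.51 × 0.75) = 0.0225/0.3825 = 5.9%.

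The first four rows assume equal correlation. Simulating the OSDI ≥ 20 entry rule at screening, still with equal correlation, lowers their range to about 7–16%.

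**4. Share of the gain due to screening.** Relative to the planned change score, the Day 1 covariate alone multiplies the variance by (1 − b²)/[2(1 − b)] = (1 + b)/2. That is a cut of 25% at b = 0.5 and 10% at b = 0.8. Take b = 0.5, where a single-visit SD of 14 also gives a change SD of 14. With 23 per arm and 12 points:

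- planned change score: 81.1%
- Day 1 covariate: 90.7% (SD 14 × √0.75 = 12.12; 43 df)
- both covariates: 90.6% under steady decay, up to 93.5% with all correlations 0.5 (42 df)

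In this example the screening value adds between nothing and about 3 percentage points of power. Most of the improvement comes from the Day 1 covariate.

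**5. Averaging the two visits instead.** The variance of change from the two-visit mean is 1 + (1 + a)/2 − (b + c). Under equal correlation this is 1.5(1 − r), which is 25% below 2(1 − r). Under steady decay over gaps of 14 and 29 days with b = 0.8, a = 0.8^(14/29) = 0.898 and c = 0.718. The variance is then 1 + 0.949 − 1.518 = 0.431 against 0.400, about 8% higher. With b = 0.4 it is about 3% lower. Averaging can therefore lose precision.

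**The case against.** **The planned test is sound.** A two-group comparison of change from Day 1 is valid, matches the stated objective and fits the sample size calculation. Nothing obliges the sponsor to use two pre-treatment values. This stands: the point concerns efficiency only.

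**Equal correlation is the favourable case.** It requires screening to predict Day 30 as well as Day 1 does, although screening lies up to two weeks further back and Day 30 follows a month of treatment. The protocol also gives reasons why screening may be less typical. Contact lenses need only be stopped one week before dosing, so a screening reading may be taken while they are still worn. Screening OSDI and TBUT also help decide eligibility. This stands, and it is why the range extends down to zero.

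**A stronger reading is tempting.** A reader might infer that averaging screening and Day 1 would cut variance by 25% and lift power from 81% to 91%. Those figures need equal correlation, and the power figure also needs SD 14 to be the SD of the change. They are measured against an unadjusted change score, so they say nothing about the gain beyond a Day 1 covariate. Averaging can also raise the variance (step 5), and it would leave the SAP with two definitions of baseline if the change tables kept Day 1. The documents do not support it.

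**Coverage is uneven.** The screening list in Protocol 3.2.2 ("screening assessments including OSDI, tear film break-up time (TBUT), and corneal and conjunctival staining are performed by the Investigator") does not name osmolarity or blink rate, and the efficacy entries for OSDI in Protocol 6.3.2 and SAP 11.1.1 omit screening. The synopsis, Table 2 and Protocol 6.3.1 show that the values are planned all the same. Some could still be missing. Since the SAP imputes nothing, an unguarded covariate would drop those subjects. That needs a rule.

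**Screening values are not wholly idle.** Protocol 7.2.4 plans descriptive summaries by visit day, and Protocol 6.3.1 makes continuation depend on there being no substantial change since screening. The accurate statement is that no treatment comparison uses them.

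**Conclusion.** The point holds as a minor, avoidable loss of precision in the Part 3 comparisons of OSDI, TBUT, osmolarity and blink rate. Staining, tested by rank sum, falls outside it.

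Beyond a Day 1 covariate, the screening value is worth 11–20% of residual variance under equal correlation of 0.5–0.8. It is worth about 0–6% under steady decay, or where screening and Day 1 correlate at 0.7–0.8 and each correlates less with Day 30. Intermediate structures fall between (8% in the 0.6, 0.5, 0.5 row). No figure in the documents selects among these cases.

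A reader might also infer that every Part 3 efficacy interval is bound to narrow, or that the trial is underpowered without this change. Neither follows. The gain can be nil, and the planned analysis meets its 80% target at 23 per arm on its own assumptions.

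**What to change.** Before database lock and code opening, amend SAP 11.1.2 and 11.2.1 as follows.

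- State that baseline is the Day 1 value before the first dose.
- In the Part 3 models for OSDI, osmolarity, TBUT and blink rate, keep change from baseline as the response. Enter the Day 1 value and the screening value of the same variable as covariates. For eye-level measures, take both from the same eye, or the same summary of eyes, as the outcome.
- State how a missing screening value is handled so that no subject is lost. For example, if any subject with Day 1 and Day 30 values lacks the screening value of a variable, that variable's model uses Day 1 only.
- Do not average the two visits. Day 1 remains the reference for the tables of change.

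The cost is a few sentences and two degrees of freedom against the planned ANOVA (44 to 42 with 46 analysed), or one against a model that already has Day 1. No visit, measurement or patient is added. If screening proves uninformative, the loss is that degree of freedom. If the rank sum fallback for non-normal data is used, neither covariate enters and the gain is forgone for that variable.
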